### 3.2.3 Outcome Measures:

Outcome measures will be assessed at several time-points throughout the study (see Figure 1). We emphasize that both moderate-intensity motor training and tDCS have been reported to have significant single-session effects. Our testing schedule will allow us to capture both the immediate effects (also referred to as “online effects” [28]), and persistent effects (or “offline effects” [28]). **Immediate Effects** will be assessed within each intervention day, prior to and following the intervention. **Persistent Effects** will be assessed by comparing baseline measures to measures obtained following the 3rd intervention day. To minimize participant burden and because single-session effects may not last for prolonged periods, only a subset of outcome measures will be collected before and after each training session. Table 1 outlines the timing of specific outcome measures to be performed in order to determine the **Immediate** and **Persistent Effects**.

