**Table 1. Outcome measures timing.**

	Baseline Measures	Immediate Effects	Persistent Effects
Walking Speed	●	●	●
Walking Distance	●		●
Balance	●		●
Fear of Falling	●		●
Ankle dorsiflex strength	●	●	●
Knee extensor strength	●		●
Functional leg strength	●		●
Spasticity	●	●	●
BDNF	●	●	●

**Walking Function:** Walking speed will be the primary outcome measure for walking function, as speed has been the standard measure used in the literature and will allow us to assess outcomes relative to other published studies. As in our prior studies, functional walking capacity will be measured based on 2-minute walk test distance.[3] The use of the 2-minute rather than the 6-minute walk test allows us to include individuals whose impairments result in inability to walk for 6 minutes. Kinematic data related to walking performance will be obtained using an accelerometer-based motion capture system (Xsens MVN Biomech Awinda, Xsens, Enschede, Netherlands) as the participant walks along a 15-meter path, using only the passive assistive devices they typically use (e.g., lower limb orthotics, walker, forearm crutches). Secondarily, we will assess gait quality as reflected by step height, step length, and step symmetry. *Appendix B* provides a detailed description of walking function test set-up and implementation.

**Balance:** Balance will be measured using the Berg Balance Scale, which has been found to be valid for use in persons with SCI. *Appendix C* provides a detailed description of balance test set-up and implementation.

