**Serum Brain-Derived Neurotrophic Factor (BDNF):** Serum concentrations of BDNF will be measured in venous blood. Venous blood samples (10 mL) will be drawn by a Shepherd Center phlebotomist and stored in pre-chilled serum venipuncture tubes. Samples will be allowed to clot for 1 hour at room temperature and 1 hour at 4°C. Serum will be separated by centrifugation (1000 x g for 15 min) and stored in Eppendorf tubes at -70°C until analysis. At least once per month, blood samples will be transported by the study coordinator by car to the Georgia Institute of Technology, Department of Applied Physiology for analyses. Blood serum samples will be analyzed for BDNF by enzyme-linked immunosorbent assay (ELISA) using *Mature Rapid ELISA* kits from Biosensis (Cat #: BEK-2211-1P/2P, Biosensis Pty Ltd., SA, Australia) with a detection range from

7.8 pg/ml to 500 pg/ml. Preparation of mature BDNF standard and other assay procedures will be followed according to manufacturer's specifications (*Appendix I*). A total of 4 blood samples will be collected for each participant, and serum BDNF concentrations (ng/ml) will be compared across the following time points: baseline (Day 1), pre-exercise (Day 2), post-exercise (Day 2), and persistent test (Day 5).

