### **6.1 Statistical Assumptions**

All data will be managed using Microsoft Excel and analyzed using SPSS. Descriptive statistics, including means, standard deviations and 95% confidence intervals of the pre-post change for each condition will be calculated for all measures. The baseline characteristics of the participants assigned to the 2 intervention groups will be compared using ANOVA and Chi-square analysis. The change from Baseline test (day 1) to Persistence test (day 5) for the two intervention groups will be compared using repeated measures ANOVA followed by pair-wise contrasts between the two groups. Pair-wise t-tests with Bonferroni correction for multiple comparisons will be used to evaluate within-day change for each of the 3 intervention days. We will identify the effect size and 95% confidence interval associated with effects to identify the outcome measures that are most sensitive to change following intervention with MT-only and MT+tDCS. We will also assess variables associated with responsiveness to intervention, using logistic linear regression to identify the variables that are most strongly associated with change in our primary outcome measure of walking function. Where significant pre/post differences exist among the primary outcome measures and blood serum concentrations of BDNF, Pearson correlation coefficients will be calculated to determine the strength of any relationship that might exist between measures of walking function and changes in BDNF concentration.

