### **8.0 Study Medication/Device/Intervention/Other Procedure Details**

Blinding: Assessors will remain blinded to participant group allocation throughout the duration of the study.

Assignment of Study Intervention: To ensure equivalence of baseline data, stratified randomization will be used to ensure equal distribution of more- and less-impaired participants between groups.

Dosing and Treatment: Participants will participate in a total 1x2-hour baseline testing session, 3x1-hour MT or MT+tDCS sessions, and 1x1hour follow-up testing session over 5 consecutive days. MT activities will take approximately 18 minutes to complete.

Identity of Medication/Device/Treatment: tDCS will be delivered using a Soterix Medical, Inc. 1x1 tDCS device.

Unblinding Procedures: Data will remain blinded throughout participant enrollment and testing. Interim data analyses will not be performed for this study. Data will be unblinded by [name] upon completion of all evaluations for all study participants.

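### Section 6.1 compares raw Day 1 to Day 5 change between conditions, with no baseline adjustment and without the Day 2 pre-training value, so the tDCS estimate loses precision

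*Combined protocol and SAP*

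**What the plan says.** Section 6.1 sets the between-condition analysis: "The change from Baseline test (day 1) to Persistence test (day 5) for the two intervention groups will be compared using repeated measures ANOVA". Contrasts of one condition against the other come after that. The section names no baseline covariate. Its regression looks for predictors of response and does not adjust the tDCS contrast.

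Section 8.0 gives the layout of each block: one baseline session, then "3x1-hour MT or MT+tDCS sessions, and 1x1hour follow-up testing session over 5 consecutive days". Section 3.2.3 says that immediate effects "will be assessed within each intervention day, prior to and following the intervention", but that "only a subset of outcome measures will be collected before and after each training session". Table 1 marks that subset as walking speed, ankle dorsiflexor strength, spasticity and BDNF. Walking speed matters most: "Walking speed will be the primary outcome measure for walking function".

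The BDNF paragraph of Section 3.2.3 confirms that Day 2 is a training day with a sample taken before exercise. In Section 6.1 the only stated use of the within-day values is in paired t-tests, which "will be used to evaluate within-day change for each of the 3 intervention days".

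Sections 3.2.1 and the Schedule of Events describe a two-period cross-over with two weeks between blocks. Section 6.2 plans for 30 completers.

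**The concern.** In a cross-over, stable differences between people cancel when a participant's two conditions are compared. Subtracting each period's Day 1 value then removes only what is specific to that period, and it adds the Day 1 measurement error to the contrast. An analysis that estimates the baseline slope removes the same nuisance variation without paying the full price in error. A second pre-training measurement would reduce the baseline error further, and for walking speed it is already collected.

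At stake are the width of the confidence interval and the power for the MT+tDCS versus MT-only comparison. That comparison is one of the two primary goals named at the end of Section 1.0. Section 6.1 also intends to report effect sizes with 95% confidence intervals, so interval width bears directly on what the study can say.

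**Working it through.** **Sample size used.** Section 6.2 gives an effect size of 0.69, power 0.8 and alpha 0.05, hence 15 for the pre-post effect. A one-sided paired t-test reproduces 15 (power 0.815). The two-sided normal formula gives ((1.960 + 0.842)/0.69)² = 16.5. The plan doubles 15 to 30, and 30 × 1.15 = 34.5 gives the 35 enrolled. Only the 30 completers (15 per sequence) are used below.

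**Within-person reading.** Take value = person + person-by-period + day error, with variances vp and ve for the last two, and scale so that vp + ve = 1. The person term cancels. Let r = vp/(vp + ve), the correlation between the between-period differences at baseline and at Day 5. The documents do not give r; I take 0 to 0.9. Day errors are assumed equal in size and independent. Up to a common factor, the variance of the tDCS contrast is:

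- raw change: 2(1 − r)
- ANCOVA on Day 1: 1 − r²
- ANCOVA on the mean of Day 1 and Day 2 pre-session: (1 − r)(1 + 2r)/(1 + r)

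So change relative to ANCOVA is 2/(1 + r) with one baseline and 2(1 + r)/(1 + 2r) with two. The simulated columns use n = 30, a period term and an estimated slope, and so include the cost of estimating it.

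| r | One baseline, formula | One, simulated | Two baselines, formula | Two, simulated |
|---|---|---|---|---|
| 0 | 2.00 | 1.91 | 2.00 | 1.92 |
| 0.3 | 1.54 | 1.50 | 1.63 | 1.59 |
| 0.5 | 1.33 | 1.29 | 1.50 | 1.45 |
| 0.7 | 1.18 | 1.13 | 1.42 | 1.38 |
| 0.9 | 1.05 | 1.01 | 1.36 | 1.32 |

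Repeat simulations agree to within about 0.03. At r = 0.5, 30 participants analysed by change are worth 30/1.29 = 23 (one baseline) or 30/1.45 = 21 (two) analysed by ANCOVA. The interval is wider by √1.29 = 1.14 or √1.45 = 1.20.

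**Between-group reading.** Here the relevant quantity is rho, the Day 1 to Day 5 correlation across people, which is also not given. ANCOVA variance relative to change is (1 + rho)/2 with one baseline and (1 + 2rho)/(2(1 + rho)) with two.

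- At rho = 0.5 these are 0.75 and 0.67.
- At rho = 0.95 they are 0.975 and 0.74. Simulated at n = 30, they become 1.00 to 1.02 and 0.75 to 0.79.

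With 15 per group and an effect of 0.69 SD of change, two-sided power is 0.45 for raw change. Both baselines raise it to 0.56 (rho 0.95) or 0.61 (rho 0.5).

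**Carry-over.** Suppose a tDCS effect of size L persists into period 2, equally at baseline and Day 5, in those who had tDCS first. Averaged over the two sequences, the MT+tDCS minus MT-only difference is shifted by −L/2 at baseline and at Day 5. With slope b the estimate is the true effect minus (1 − b)L/2, so raw change (b = 1) is unaffected.

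- Day 1 ANCOVA has b = r. With L equal to half the true effect, it returns 1 − 0.25(1 − r) of that effect: 0.83, 0.88 and 0.93 at r = 0.3, 0.5 and 0.7.
- With both baselines b = 2r/(1 + r), which gives 0.87, 0.92 and 0.96.

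Simulation gives the same values. The amount of carry-over is an assumption; the documents give none.

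**The case against.** **Raw change is a defensible trade of variance for bias.** Participants train in both blocks and have only two weeks between them. A constant carry-over drops out of raw change but pulls ANCOVA toward zero, most strongly at low r, where the precision gain is largest. This stands. It is a reason to keep raw change as a sensitivity analysis, but it does not show that raw change should be the only analysis.

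**The size is not anchored.** No correlation is given, and Section 6.1 does not say whether the contrast is within-person or between groups; Section 6.2 speaks of 15 per group. This also stands. A reader might infer that the planned analysis doubles the variance, but that holds only near r = 0 on the within-person reading.

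**BDNF.** Table 1 might suggest that BDNF also has two baselines in each period. The BDNF paragraph lists "baseline (Day 1), pre-exercise (Day 2), post-exercise (Day 2), and persistent test (Day 5" as the time points, and both that paragraph and Appendix I give four samples per participant in total. That covers one five-day block, so a second baseline in both periods cannot be assumed.

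**The Day 2 value is not wasted.** It serves the within-day tests and is missing only from the Day 1 to Day 5 comparison. Its timing is read from the text, since Figure 1 was not available. Section 3.2.2 places a maximal exercise test in baseline testing, so equal error on Days 1 and 2 is unverified.

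**The study is preliminary, and Section 6.2 puts the training effect first.** For the pre-post training estimate, raw change is the natural measure. The fix leaves that estimate alone.

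**Conclusion.** The point holds as a loss of precision in the tDCS contrast. A reader might infer that the comparison is biased or the test invalid; nothing in the documents supports that.

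On the within-person reading, the planned analysis has about 1.9 to 1.0 times the variance of ANCOVA on Day 1, and about 1.9 to 1.3 times that of ANCOVA on both baselines, for r from 0 to 0.9. On a between-group reading with very stable walking speed, Day 1 adjustment alone gains almost nothing, and the saving of roughly 25% comes from the second baseline.

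These figures rest on 30 completers, on assumed correlations, and on equal, independent day errors for the two-baseline results. The direction is secure for walking speed. Outcomes measured only on Days 1 and 5 can gain only from Day 1 adjustment. The change is worth making before unblinding.

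**What to change.** In Section 6.1:

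- Make the Day 5 value the outcome of the between-condition analysis, with a period term and with the period-specific baseline and the participant's mean baseline as covariates. The slope is then estimated on the within-person baseline difference.
- For walking speed, ankle dorsiflexor strength and spasticity, define the period baseline as the mean of Day 1 and the Day 2 pre-session value. Do the same for BDNF only if it is sampled in both periods. Use Day 1 alone for the other outcomes.
- Report the adjusted MT+tDCS minus MT-only difference with its 95% confidence interval.
- Keep raw change for the pre-post training estimate and as a sensitivity analysis for the tDCS contrast. State that the adjusted estimate would be pulled toward zero if a tDCS effect outlasts the two-week break.

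The cost is SAP wording, one or two degrees of freedom and that exposure to carry-over. No new visits or measurements are needed.

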A preponderance of the evidence suggests that corticospinal drive is increased by **combining** moderately intense motor training with stimulation of supraspinal centers. This notion is supported by research demonstrating that intensive motor training aimed at increasing corticospinal drive improves muscle activation and walking function.[15] Furthermore, non-invasive brain stimulation has been shown to improve lower extremity strength, lower-limb control, gait, and balance.[16-19] Cortical stimulation with repetitive transcranial magnetic stimulation (rTMS) has been associated with improved walking function in persons with SCI [20], although this form of stimulation has inherent drawbacks that limit its use in clinical settings. An alternative to rTMS is transcranial direct current stimulation (tDCS), which is a low-risk, non-invasive brain stimulation technique involving low-intensity currents delivered to the motor cortex and aimed at modulating cortical excitability. tDCS is affordable and lacks many of the drawbacks associated with rTMS, making it a more clinically accessible technology. Emerging studies in persons with stroke have combined tDCS with moderately intense motor training and have demonstrated increased dorsiflexor control,[16] quadriceps strength,[17, 18] and balance.[17] tDCS may also have the capacity to modulate excitability of spinal networks and to decrease spasticity.[21, 22]

Based on the evidence described above, we put forward two primary goals of the proposed project: *1) determine whether a moderate-intensity training program designed to increase control of gait-related movements can improve functional and neurophysiologic measures, and 2) determine whether training-related responses are larger when training is augmented with cortical stimulation to increase supraspinal drive.*

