## 2.0 Study Aims and Hypotheses:

### 2.1 Aim 1. *Quantify effects of moderate-intensity motor training alone (MT-only group) and moderate-intensity motor training + tDCS (MT+tDCS group) on walking function and balance.*

We hypothesize that training will be associated with improvements in locomotor function (walking speed and step height), balance (Berg Balance Test), and leg muscle strength (quadriceps and plantarflexor muscles). We also hypothesize that gains in the MT+tDCS group will be larger than those of the MT-only group.

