#### Schedule of Events:

[figure not shown]
Individuals will be asked to participate in the study over two, 5 consecutive day periods. Following completion of the fifth day, participants will be asked to take 2 weeks off before returning to the lab to repeat the intervention schedule but in the opposite group in which they originally participated (i.e. MT-only to MT+tDCS; MT+tDCS to MT-only). A detailed schedule of events including testing and intervention timing is provided in Figure 1.

**Figure 1.** Timing of intervention and outcome measures.

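### Section 6.1 states no direct MT+tDCS versus MT-only comparison for within-day change, and no explicit confidence interval for the between-condition difference in either time frame

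*Combined protocol and SAP*

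**What the plan says.** Section 6.1 treats the two time frames differently.

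- **Persistent change.** "The change from Baseline test (day 1) to Persistence test (day 5) for the two intervention groups will be compared using repeated measures ANOVA". Pair-wise contrasts between the two groups follow.
- **Immediate change.** "Pair-wise t-tests with Bonferroni correction for multiple comparisons will be used to evaluate within-day change for each of the 3 intervention days". The sentence does not say what is compared with what.

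Section 6.1 has two statements on confidence intervals. The first is per condition: "95% confidence intervals of the pre-post change for each condition will be calculated for all measures". The second promises effect sizes with 95% intervals for effects that it does not define. Its stated purpose is to find the outcome measures that respond most to the two interventions.

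Section 3.2.3 says that immediate effects "will be assessed within each intervention day, prior to and following the intervention". Table 1 marks four of its nine outcomes for immediate testing: walking speed, ankle dorsiflexor strength, spasticity and BDNF. Walking speed is named as the primary measure of walking function.

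The design is a cross-over. After two weeks off, participants "repeat the intervention schedule but in the opposite group in which they originally participated".

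**The concern.** The second goal in Section 1.0 is to "determine whether training-related responses are larger when training is augmented with cortical stimulation to increase supraspinal drive". Section 2.1 adds: "We also hypothesize that gains in the MT+tDCS group will be larger than those of the MT-only group". Section 2.2 says the same for strength and spasticity. None of these is limited to Day 5. Section 3.2.3 gives the single session its own weight: "We emphasize that both moderate-intensity motor training and tDCS have been reported to have significant single-session effects". The testing schedule is built to capture those effects.

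The trial therefore collects, in each participant and under both active and sham stimulation, the data needed to estimate what tDCS adds within a session. If the t-tests are pre versus post, the stated analysis does not use the data for this. It gives one result per condition and day, and the reader must set the two conditions side by side. A pre-post test in the MT+tDCS condition mixes the effects of training, of stimulation and of repeated testing, so it is not evidence on stimulation. If a between-condition test is intended, the plan needs to say so; otherwise the choice stays open until after unblinding.

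**Working it through.** The point is mainly textual, and the plan gives no figure of its own for this contrast. The passages come first, then an illustration of why the planned intervals do not fill the gap.

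**1. The text**

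| Time frame | Stated test | Between-condition comparison stated? | Interval for the difference stated? |
|---|---|---|---|
| Day 1 to Day 5 | Repeated measures ANOVA, then contrasts between groups | Yes | Not explicitly |
| Within day | Bonferroni-corrected pair-wise t-tests, by day | No; comparator not named | Not explicitly |

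The two analysis sentences in 6.1 are adjacent, and only the first mentions the two groups. The object of the second is within-day change, which Section 3.2.3 defines by measurements before and after the session. No other section supplies the contrast.

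**2. Inputs for the illustration**

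- n = 30 completers. Section 6.2 requires 30 and enrols 35 for 15% attrition (35 × 0.85 = 29.75). In the cross-over, each completer contributes both conditions.
- The SD of the change being analysed is taken as equal in the two conditions and set to 1. This is an assumption.
- ρ is the correlation between a participant's two changes. The documents do not give it, so 0, 0.3, 0.5 and 0.7 are assumed.

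**3. Interval for the difference, paired**

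The variance of a participant's difference is 1 + 1 − 2ρ = 2(1 − ρ). The 95% half-width is t(29) × √(2(1 − ρ)/30), with t(29) = 2.045.

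- ρ = 0: 2.045 × √(2.0/30) = 0.528
- ρ = 0.3: 2.045 × √(1.4/30) = 0.442
- ρ = 0.5: 2.045 × √(1.0/30) = 0.373
- ρ = 0.7: 2.045 × √(0.6/30) = 0.289

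**4. What the per-condition intervals give**

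Each per-condition half-width is 2.045/√30 = 0.373. Combined as if independent, the half-width is √(0.373² + 0.373²) = 0.528, whatever ρ is. The ratio to the paired half-width is 1/√(1 − ρ).

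| Assumed ρ | Paired half-width (SD) | Combined as independent (SD) | Excess width |
|---|---|---|---|
| 0 | 0.53 | 0.53 | none |
| 0.3 | 0.44 | 0.53 | 20% |
| 0.5 | 0.37 | 0.53 | 41% |
| 0.7 | 0.29 | 0.53 | 83% |

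The planned per-condition intervals carry no information on ρ, so a reader cannot recover the correct interval from them. Adjusting for period costs one degree of freedom and changes these figures little.

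**The case against.** **The defect may be only ambiguity.** The preceding sentence in 6.1 speaks of pair-wise contrasts between the groups, and the pair-wise t-tests could carry the same comparator. A t-test between conditions on change scores would fit the words. This stands in part: the comparison is unstated, not shown to be excluded. A reader might infer that the plan rules out a within-session comparison, and the text does not support that.

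**The second interval statement might cover it.** The intervals for unspecified effects are not limited to single conditions or to Day 5. But their stated use is to find the outcomes most sensitive to change, and the sentence does not promise a difference between conditions.

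**The consequence is limited.** This stands. The hypotheses are not tied to single sessions, Section 6.2 puts the primary interest in training, and Section 3.2.1 seeks preliminary evidence. All four affected outcomes keep a stated between-condition comparison of persistent change. A reader might infer that the tDCS hypotheses have no test at all; they do, at Day 5.

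**The plan does not propose to judge tDCS by comparing significance.** This also stands. A reader might infer that tDCS would be declared effective if only the MT+tDCS condition reached significance. That would be unsound, but nothing in 6.1 says that it will be done. Nor does the plan propose to combine the per-condition intervals as if independent. At positive correlation that would err on the wide side.

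**Conclusion.** The point holds, at minor to moderate severity. Section 6.1 states a comparison of the two conditions for Day 1 to Day 5 change only. For within-day change, on the natural reading, it gives no direct test or interval of what tDCS adds, including for walking speed. It might be inferred that Day 1 to Day 5 change already has a stated interval for the difference. It has a stated comparison, but no explicit interval.

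This is more than missing detail, because a within-participant contrast on data already collected answers the question and the stated t-tests do not. Its reach is one time frame of the second goal.

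The conclusion about the text rests on reading the t-tests as pre versus post. The half-widths of 0.29 to 0.53 SD rest on 30 completers of both periods, equal SDs and assumed correlations. They illustrate the gap, and the finding does not depend on them.

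**What to change.** In Section 6.1:

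1. Name the comparator of the within-day t-tests.
2. For the immediate-effect outcomes, walking speed first, pre-specify the within-participant MT+tDCS minus MT-only difference in post-minus-pre change, averaged over the three intervention days and adjusted for period, with its 95% confidence interval. For BDNF use Day 2 only. Section 3.2.3 gives four samples per participant in total, so state whether both periods are sampled; if only one is, the BDNF contrast can only be between randomised groups.
3. Use the day-specific pre-post t-tests as evidence on training only.
4. State the 95% interval of the between-condition difference for Day 1 to Day 5 change as well.

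The cost is SAP wording and a little analysis, with no new visits or participants. What is given up is the use of day-specific pre-post p-values to support a claim about tDCS.

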First, evidence from a large multi-million dollar locomotor training study involving persons with stroke found that a well-designed exercise program can be as effective for improving walking function as an intensive locomotor training program.[6] Second, a single session of moderate-intensity exercise has been found to promote motor skill acquisition, presumably through neurotrophic mechanisms, and to reduce spasticity.[7-9] In persons with SCI, 10 minutes of moderate-intensity activity (54% of maximal heart rate) was associated with a 1.5-fold increase in serum levels of neurotrophic factor.[7] Studies investigating locomotor training in persons with SCI [10] and in spinal rats suggests that exercise can restore the endogenous inhibition that is lost after SCI [11], which may affect the extent and severity of spasticity.[9] Third, supraspinal centers are known to be involved in locomotion, yet studies aimed at improving walking function have focused almost exclusively on activation of spinal circuits.[12] In rodent models with SCI, evidence indicates that recovery of locomotor function depends largely on activation of spared supraspinal pathways [13] and that there is an increased amplitude of lower limb motor evoked potentials following intensive locomotor training in humans with SCI.[14] These studies suggest a relationship between the strength of corticospinal drive and walking function. Therefore, it seems plausible that walking function can be improved by increasing the effectiveness and activation of spared descending pathways.

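### The BDNF–walking correlation is computed only after significant pre/post change, and the responsiveness regression is not defined (minor; supportive analyses only)

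*Combined protocol and SAP*

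**What the plan says.** **Correlation.** Section 6.1 says: "Where significant pre/post differences exist among the primary outcome measures and blood serum concentrations of BDNF, Pearson correlation coefficients will be calculated". The stated purpose is to measure how strongly walking function and BDNF change are related. The wording does not settle whether both changes must be significant or whether one is enough. It also does not say which BDNF change is meant or how the two conditions are handled.

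**Regression.** Section 6.1 studies responsiveness "using logistic linear regression to identify the variables that are most strongly associated with change in our primary outcome measure of walking function". Section 3.2.3 says: "Walking speed will be the primary outcome measure for walking function". Appendix B records the 10-metre walk in seconds. No walking-speed responder cut-off appears in the text.

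**Timing.** Section 3.2.3 defines two contrasts. The Immediate contrast compares values from before and after the session on the same training day. The Persistent contrast "will be assessed by comparing baseline measures to measures obtained following the 3rd intervention day". Table 1 lists walking speed and BDNF for both. Section 3.2.3 (serum BDNF) and Appendix I give four blood samples in total per participant: Day 1, before and after exercise on Day 2, and Day 5. Section 3.2.1 (Schedule of Events) gives each participant two five-day periods, one per condition. The text does not say which period supplies the four samples. Figure 1 was not visible in the copy reviewed and may say.

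**The concern.** A significant mean change is a different question from whether participants with larger BDNF changes also have larger walking changes. If BDNF rises in some people and falls in others, the mean change can be near zero while the individual changes still track walking speed. The condition would then suppress the only planned analysis that links BDNF to walking, for a reason unrelated to that link.

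The regression term names two models with different outcomes. An analyst who took the logistic half would have to supply a cut-off that the plan does not give, possibly after seeing the data.

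The stakes are modest. The aims in section 2.0 name neither BDNF nor predictors of response, and the MT+tDCS versus MT-only comparison rests on the repeated measures ANOVA.

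**Working it through.** The documents give no power or sample size for either analysis, so there is no planned figure to reproduce.

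**1. Inputs.** From section 6.2: 30 evaluable participants, walking effect size d = 0.69, alpha 0.05 (taken as two-sided). Assumed: the BDNF effect size, because section 1.0 says only that a single bout "was associated with a 1.5-fold increase in serum levels of neurotrophic factor", with no SD to convert it, and no Day 1 to Day 5 size is given. The range tried is d = 0 to 1.0. True correlations of 0.3 and 0.5 are also assumptions.

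**2. Effect of the condition.** Each setting used 100,000 simulated trials with bivariate normal changes. The condition was an uncorrected one-sample t test on each change, followed by the Pearson test. Entries are the chance that the correlation is computed and significant.

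| BDNF d | r = 0.5, both | r = 0.5, either | r = 0.3, both | r = 0.3, either |
|---|---|---|---|---|
| 0 | 0.03 | 0.79 | 0.01–0.02 | 0.35 |
| 0.3 | 0.28 | 0.79 | 0.12 | 0.35 |
| 0.5 | 0.60 | 0.80 | 0.26 | 0.36 |
| 0.69 | 0.76 | 0.82 | 0.34 | 0.37 |
| 1.0 | 0.79 | 0.83 | 0.35 | 0.37 |

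Without the condition the values are 0.83 (r = 0.5) and 0.37 (r = 0.3). At BDNF d = 0.3 and r = 0.5 the 'both' condition is met in about 0.35 of trials, which accounts for most of the drop from 0.83 to 0.28.

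**3. Error rate and bias.** At true r = 0, the rejection rate among trials that pass the 'both' condition is 0.049 to 0.051. At true r = 0.5 the mean estimate among passing trials is 0.463 to 0.492, against 0.494 unconditionally. The condition therefore inflates neither.

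**4. What an unconditional report gives.** The 95% CI is tanh(atanh(r) ± 1.96/√(n − 3)), and 1.96/√27 = 0.377.
- Observed r = 0.3: tanh(0.310 ± 0.377) = −0.07 to 0.60.
- Observed r = 0.5: tanh(0.549 ± 0.377) = 0.17 to 0.73.

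The interval is informative whether or not the test is significant.

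**5. Why removing the condition is not enough.** Suppose BDNF comes from one period, 15 participants per condition are pooled, and tDCS shifts both changes by δ SD, with no correlation within condition. The pooled correlation is (δ²/4)/(1 + δ²/4).
- δ = 0.69: 0.119/1.119 = 0.11.
- δ = 1.0: 0.25/1.25 = 0.20.

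Simulation at n = 30 rejects in about 9% and 19% of trials. Section 6.2 assumes an additive or larger tDCS effect on walking; the BDNF shift is an assumption made here. Condition must therefore be handled explicitly.

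**6. Regression.** Set side by side, the passages give a continuous outcome, a model name containing both logistic and linear, and no cut-off. No calculation is needed.

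**The case against.** Running a mechanistic follow-up only once the measures have moved is a recognisable way to limit exploratory correlations, and the BDNF change itself is reported regardless: section 6.1 gives means, SDs and 95% CIs of change for all measures. That stands, and it keeps the point minor. It does not make the condition fit the stated purpose.

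The simulated condition is only a stand-in for the plan's own tests, which use Bonferroni correction within days and repeated measures ANOVA for Day 1 to Day 5. No single-session effect size is documented, so the figures do not size the Immediate contrast. The most extreme values need a BDNF change of exactly zero and the stricter reading. All of this stands, which is why the result is given as a range.

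On the regression, a reader might infer that the plan has simply misnamed a linear model. The documents do not show that: responsiveness could mean an intended responder analysis. What they show is an undefined model, and it needs defining under either intention.

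A reader might also infer that selecting on significance produces false positives or exaggerated correlations. Step 3 shows that it does not. The false-positive risk in step 5 comes from pooling conditions, not from the condition on significance.

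**Conclusion.** The point holds as a minor one, confined to supportive analyses. The condition can hide a real BDNF–walking association. The loss is serious only if both changes must be significant and the BDNF change is small: about 0.28 against 0.83 at assumed BDNF d = 0.3 and true r = 0.5. Under the 'either' reading the loss is at most about 0.04. With BDNF d of 0.69 or more it is 0.04 to 0.07 at r = 0.5, even under 'both'. These figures rest on n = 30, walking d = 0.69, normal changes and an uncorrected t-test condition. The regression is ambiguous as written, and no size is attached to that part because any power loss would depend on a cut-off the documents do not give. Neither part affects type I error, the comparison of MT+tDCS with MT-only, or the sample size.

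**What to change.** **Correlation.** In section 6.1, delete the opening condition on significance. Report, labelled exploratory, the Pearson correlation with its 95% CI between change in the walking measures (speed first) and change in BDNF, for the Immediate contrast (Day 2 before to after exercise) and the Persistent contrast (Day 1 to Day 5). State which cross-over period the four BDNF samples come from, and pair BDNF and walking changes from the same period and condition. Adjust for condition by partial correlation, or report by condition; do not pool.

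**Regression.** Replace the model name with linear regression of Day 5 walking speed on Day 1 speed, impairment stratum, condition, period and candidate predictors named before unblinding. Include a participant random effect, because each person contributes two periods. Keep a logistic model only as a secondary analysis, with its responder cut-off fixed before unblinding.

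**Cost.** A few sentences and an amendment, which sections 7.3 and 7.4 send to the IRB for approval before it takes effect. Section 8.0 leaves room for this: "Data will remain blinded throughout participant enrollment and testing". No new data are needed.
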